## Protocol

**Protocol:**

Temporomandibular disorders (TMD) are musculoskeletal disorders that are commonly encountered, with pain in the temporomandibular joint (TMJ) and jaw closing muscles. Pain that involves the temporomandibular joint includes inflammatory pathologies such as arthritis, painful disk displacements and many times have an overlay of psychosocial comorbidities due to the uncontrolled pain. TMJ osteoarthritis is an intracapsular condition affecting the temporomandibular joint and presents with remodeling of the TMJ articulating tissues including the condyle and articular eminence secondary to inflammation resulting in intracapsular pain. There is a paucity of information regarding the relative effectiveness of different therapies for the treatment of patients with TMJ osteoarthritis. The identification of the least invasive and most efficacious therapy is vital to proper management of these patients with temporomandibular joint pain and disability. The purpose of this study is to establish the relative efficacy of TMJ arthrocentesis with steroid supplementation (a known effective therapy) compared to TMJ arthrocentesis with a supplement of plasma rich in growth factors (PRGF) for patients with TMJ osteoarthritis. Plasma rich in growth factors is isolated from the patient's own blood and injected into the temporomandibular joint to activate stem cells that may restore some of the articulating tissues that were lost during degeneration changes within the joint secondary to osteoarthritis. Pain and disability will be assessed using standard pain and physical measures that are recorded before and after treatment. Patients enrolled into the study will be examined and treated at the Department of Oral and Maxillofacial Surgery Faculty/Resident clinic. At the first appointment, they will be examined following standard procedures (medical history, physical exam, imaging by cone beam computerized tomography (CBCT)) to determine their diagnosis(es) and if they would potentially benefit from the TMJ arthrocentesis procedure. If the patient meets the inclusion criteria for the study and with their informed consent on the day of their TMJ arthrocentesis procedure, they will be required to have a pregnancy test if below age 60 and complete a questionnaire about their physical and pain symptoms and undergo a standardized clinical exam. The patients will then undergo the standard clinical protocol for TMJ arthrocentesis followed by either a 2 cc steroid/bupivacaine hydrochloride supplementation (standard treatment group) or a 2 cc PRGF supplementation (experimental group) into the TMJ. Follow-up appointments will be conducted at 1 month, 3 months and 6 months when the pain VAS measures and a clinical exam will be assessed. If patients have not experienced improvement in their primary outcome measure (TMJ pain) at the 3 month evaluation, the patient will have a second TMJ arthrocentesis procedure that will be supplemented with the alternative medication/growth factors (steroid or PRGF) using a cross-over design. Data from these patients will be analyzed separately from patients that complete the six month study. Also at 6 months, a second CBCT image of the temporomandibular joints will be obtained to determine the extent of bone remodeling within the TMJ. The results of this study should provide new information on the efficacy of PRGF supplementation for management of temporomandibular joint osteoarthritis.

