Clinical Trial Number: NCT04731233

Title: A Randomized, Double-Blind Study of the Efficacy of Platelet-Rich Growth Factor (PRGF) Supplementation Compared to Steroid Supplementation After Temporomandibular Joint (TMJ) Arthrocentesis in Female Patients With TMJ Osteoarthritis (OA)

Date: January 2, 2025

Proposed Statistical Analyses

Statistical Analyses

Statistical analyses will consist of descriptive statistics (mean, standard deviation for parametric data; median and range for non-parametric data) and inferential statistics (two way ANOVA, 1 between (treatment groups), 1 within (time)) using a probability level of < 0.05). The primary outcome variable will be intracapsular pain.

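### A month-6 comparison without the patients switched at month 3 is selected on the primary outcome, is not the randomised comparison, and can be biased in either direction

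*Protocol*

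**What the plan says.** The Protocol sets the visits: "Follow-up appointments will be conducted at 1 month, 3 months and 6 months". The switch depends on the primary outcome: "If patients have not experienced improvement in their primary outcome measure (TMJ pain) at the 3 month evaluation", then "the patient will have a second TMJ arthrocentesis procedure", which is "supplemented with the alternative medication/growth factors (steroid or PRGF) using a cross-over design". The analysis rule follows: "Data from these patients will be analyzed separately from patients that complete the six month study". A second CBCT is also taken at 6 months.

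The SAP carries a randomised, double-blind title that does not mention a cross-over. Its only inferential method is "inferential statistics (two way ANOVA, 1 between (treatment groups), 1 within (time)) using a probability level of < 0.05", with intracapsular pain as the primary outcome. It does not mention switchers, an analysis population or a primary time point. Neither document defines how large a change counts as improvement.

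**The concern.** Randomisation makes the two arms comparable at entry. Removing patients because of their month-3 pain breaks that for every later comparison, since different kinds of patient may be removed from each arm. The month-6 CBCT comparison is exposed in the same way as pain.

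The method in the SAP could spread the problem backwards. A repeated-measures ANOVA in its standard form needs every visit for each patient. If it is run on completers only, switchers' months 1 and 3 go too, and those are the only follow-up visits before the switch.

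The cross-over label raises a second, lesser issue. Only non-improvers switch. None of them stays unswitched, repeats the same product or is re-randomised. A fall in pain afterwards mixes regression to the mean, natural course, a late effect of the first product, the repeat procedure and the second product. Comparing the two directions of switch does not separate these, because each group was selected by its response to a different first product.

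**Working it through.** The documents contain no SD, correlation, effect size, sample size or expected switch rate, so there is no figure of the plan's to reproduce. The structural point rests on the text. The calculation below only shows what the selection can do.

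**Assumed inputs.** VAS 0-10; baseline SD 2; rho = 0.5, the share of baseline variance that is stable within a patient; the first procedure lowers pain by T, normal with mean mu and between-patient SD tau, equally at months 3 and 6; the second procedure has zero effect; a patient switches if month-3 pain is at or above baseline.

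**Formulas.** Visit-noise variance v = SD²(1 − rho) = 4 × 0.5 = 2. The change to month 3 has mean −mu and variance s² = tau² + 2v. Let phi and Phi be the normal density and distribution function.

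- Switch rate = Phi(−mu/s)
- M = phi(mu/s)/Phi(mu/s) and L = phi(mu/s)/Phi(−mu/s)
- Non-switchers' mean change to month 6 = −mu − (tau² + v)M/s
- Non-switchers' mean change to month 3 = −mu − sM
- Switchers' fall from month 3 to month 6 = vL/s

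**Results for non-switchers.**

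| mu | tau | s | M | (tau² + v)/s | Change to month 6 |
|---|---|---|---|---|---|
| 2 | 1 | 2.236 | 0.328 | 1.342 | −2 − 0.44 = −2.44 |
| 3 | 1 | 2.236 | 0.178 | 1.342 | −3 − 0.24 = −3.24 |
| 2 | 0 | 2.000 | 0.288 | 1.000 | −2 − 0.29 = −2.29 |
| 3 | 2 | 2.828 | 0.266 | 2.121 | −3 − 0.56 = −3.56 |
| 2 | 2 | 2.828 | 0.409 | 2.121 | −2 − 0.87 = −2.87 |
| 3 | 0 | 2.000 | 0.139 | 1.000 | −3 − 0.14 = −3.14 |

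**Month-6 gap without switchers** (from unrounded values):

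| Mean effects | tau in each arm | True gap | Gap shown |
|---|---|---|---|
| 2 vs 3 | 1 vs 1 | 1.0 | 0.80 |
| 2 vs 3 | 0 vs 2 | 1.0 | 1.28 |
| 2 vs 3 | 2 vs 0 | 1.0 | 0.27 |
| 2 vs 2 | 0 vs 2 | 0 | 0.58 |

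**If earlier visits are lost too** (tau 1 in both arms): −2 − 2.236 × 0.328 = −2.73 against −3 − 2.236 × 0.178 = −3.40, a month-3 gap of 0.66 instead of 1.0.

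**Switchers** (mu 2, tau 1): 18.6% switch. L = 1.441, so their pain falls by 2 × 1.441/2.236 = 1.3 points from month 3 to month 6 although the second procedure does nothing.

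**Range.** With equal tau in both arms (0 to 2), rho 0.3 to 0.7, and effects 1 vs 2 or 2 vs 3, the true month-6 gap of 1.0 appears as 0.60-0.90. If improvement means a 30% reduction (by simulation, rho 0.5), the three unequal-tau rows become about 1.5, −0.2 and 0.9, so the sign can reverse.

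**Mixed-model option.** This was checked by regressing month-6 pain on arm, baseline and month-3 pain in non-switchers, then standardising to all patients. With equal tau it recovers the true gap (0.99-1.01). With unequal tau (0 vs 2, or 2 vs 0) and slopes common to both arms, it gives about 0.24 for a true 0, and 1.19 or 0.80 for a true 1.0. Arm-specific slopes recover the truth under this normal model.

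**The case against.** Three replies on the sponsor's behalf have weight.

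- **No claim for the second product is announced.** The Protocol's stated purpose is the relative efficacy of the two supplements, and it keeps switchers' data apart. A reader might infer from the cross-over label that the trial plans to show that the second product works. The documents do not say so. This stands, so the label is the secondary point: it invites a reading that the SAP does not exclude.
- **Loss of months 1 and 3 is not stated.** Separate analysis may refer only to post-switch data, and no document names month 6 as the primary time point. This stands too. The loss is conditional on running the ANOVA in complete-visit form on completers only. But neither document says that the earlier visits are kept.
- **The bias might be thought conservative.** A reader might infer that dropping non-improvers from both arms only shrinks a real difference and cannot create a false one. That holds in the cases worked above with the same variability of effect in both arms. The Protocol gives no ground for assuming this, and it describes PRGF as acting by a distinct route, to "activate stem cells that may restore some of the articulating tissues that were lost". With unequal variability the same formulas give overstatement, near-disappearance of a true gap, or a false gap.

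The magnitudes rest on assumed inputs. That limits what can be said about size, not the finding that selection occurs.

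**Conclusion.** The concern holds for selection. Followed as written, the Protocol leaves a completers-only month-6 comparison, for pain and for CBCT remodeling, in groups defined by the month-3 primary outcome. The comparison protected from the switch is the one up to month 3 in all randomised patients, and neither document secures it.

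Confidence is high on the structure. Size and direction cannot be determined from the documents; the gaps of 0.80, 1.28, 0.27 and 0.58 are illustrations under a normal model with a lasting first effect and no second effect. They suffice to show that the bias is not reliably conservative. The cross-over label is a wording fault with a real but lesser risk of misreading. The change should be made; it is not a reason to doubt the randomised comparison at month 3 if all patients are kept in it.

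**What to change.** 1. In the SAP, analyse all randomised patients in their randomised arm, retain switchers' 1- and 3-month data, and report the month-3 comparison in all randomised patients as the one unaffected by the switch.
2. Do not present a completers-only month-6 comparison (pain or CBCT) as the randomised result; if shown, label it conditional on not switching. State one rule for switchers at month 6:
   - their observed month-6 value, which compares strategies that include the switch;
   - non-improvement counted as failure; or
   - a likelihood-based mixed model with post-switch values set to missing. This extrapolates, because no non-improver is seen unswitched, and it needs arm-specific relations between earlier and later pain.
3. Replace the cross-over label with 'non-randomised second treatment in non-improvers', and report post-switch data descriptively by sequence, without an efficacy claim for the second product.

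The cost is Protocol and SAP wording plus one stated rule, with no new data. The downside is that the month-6 result becomes a comparison of strategies, a responder-type result or a model-dependent estimate, and no inferential claim is made from the switchers. The treatment that non-improvers receive is a clinical matter and is not questioned.

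### On its most natural reading the protocol drops patients unimproved at 3 months from the PRGF-versus-steroid comparison, which biases it if enough patients fail to improve and the arms differ in 3-month improvement

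*Protocol*

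**What the plan says.** The aim is comparative. The protocol states: "The purpose of this study is to establish the relative efficacy of TMJ arthrocentesis with steroid supplementation", set against the same procedure with PRGF. The SAP title describes "A Randomized, Double-Blind Study of the Efficacy".

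The protocol schedules pain at three visits after treatment: "Follow-up appointments will be conducted at 1 month, 3 months and 6 months when the pain VAS measures" and a clinical examination are done. The trigger for a second procedure is the primary outcome itself: "If patients have not experienced improvement in their primary outcome measure (TMJ pain) at the 3 month evaluation", the patient has another arthrocentesis, "supplemented with the alternative medication/growth factors (steroid or PRGF) using a cross-over design". No threshold for improvement is given. The rule at issue follows directly: "Data from these patients will be analyzed separately from patients that complete the six month study".

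The SAP (Statistical Analyses) makes intracapsular pain the primary outcome and gives one inferential method: "two way ANOVA, 1 between (treatment groups), 1 within (time". It states no analysis population, no primary time point, and no handling of crossed-over patients or missed visits. The protocol also does not say whether crossed-over patients provide 6-month pain scores, or whether they are included when it says "Also at 6 months, a second CBCT image of the temporomandibular joints will be obtained".

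**The concern.** Randomisation makes the two arms comparable only if the patients compared are those who were randomised. Here the patients set aside are the ones who did badly on the primary outcome, and each arm loses as many as it produces. If one supplement leaves more patients unimproved, more of its poor results disappear, and the two remaining groups look more alike than the treatments are. If the arms differ in speed or spread of response instead, the same filter can produce a difference that does not exist. Because improvement has no threshold, the set that remains cannot be reproduced from the plan.

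The stated purpose, relative efficacy, rests on this comparison, and nothing in the SAP returns these patients to their randomised arm.

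**Working it through.** **The plan's own figures.** There are none to reproduce. The documents give no sample size, SD, response rate, effect size or threshold. What follows illustrates the mechanism only.

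**Inputs, all assumed.** Improvement from baseline at 3 and 6 months is bivariate normal on a 0-10 VAS with SD 2 and correlation rho from 0.3 to 0.9. Improved means any fall (c = 0). Mean improvement *m* is the same at 3 and 6 months unless stated otherwise.

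**Formulae.** With a = (m3 − c)/SD3:
- share retained = Φ(a)
- mean 6-month improvement among those retained = m6 + rho × SD6 × φ(a)/Φ(a)
- mean 3-month improvement among those retained: the same, with rho = 1 and 3-month values.

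**Step 1: mean improvement 1 vs 2.** Here a = 0.5 and 1.0, so φ/Φ = 0.5092 and 0.2876. The retained difference is 1 − rho × 2 × (0.5092 − 0.2876) = 1 − 0.443 × rho. This is 0.56 at 3 months (rho = 1). At 6 months it is 0.87, 0.78 and 0.60 for rho 0.3, 0.5 and 0.9.

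**Step 2: a true difference of 1.0 at other response levels.**

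| Mean improvement | Retained | 3 months | 6 months, rho 0.3 to 0.9 |
|---|---|---|---|
| 1 vs 2 | 69% vs 84% | 0.56 | 0.87 to 0.60 |
| 2 vs 3 | 84% vs 93% | 0.70 | 0.91 to 0.73 |
| 3 vs 4 | 93% vs 98% | 0.83 | 0.95 to 0.85 |

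A simulation of the 1 vs 2 case (0.5 vs 1.0 in SD units, rho 0.5) gave 0.279 and 0.388 SD. Multiplied by 2, these are 0.56 and 0.78, as in step 1.

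**Step 3: false differences.**
- Equal mean improvement of 2, SD 2 vs 3: the retained 3-month means differ by 0.71. At 6 months the difference is 0.71 × rho, or 0.21 to 0.64, favouring the more variable arm.
- 3-month improvement 2 vs 1, equal at 6 months: the false 6-month difference is 0.443 × rho, or 0.13 to 0.40, favouring the slower arm.

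**Step 4: where there is no bias.**
- Identical arms: difference 0.
- Equal at 3 months (2 and 2) and 1.0 apart at 6 months: the φ/Φ terms cancel and the difference stays 1.00 at every rho.
- rho = 0: the 6-month difference stays 1.00.
- Almost nobody unimproved: Φ(a) approaches 1, φ(a)/Φ(a) approaches 0, and the bias vanishes.

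**Step 5: the missing threshold matters.** If improved meant a fall of more than 2 points (c = 2), then at rho 0.5 to 0.9 the 6-month difference would be 0.66 to 0.38 for 1 vs 2, against 0.78 to 0.60 with any fall. For 3 vs 4 it would be 0.78 to 0.60, against 0.92 to 0.85.

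**The case against.** The strongest objection is that the point hangs on one sentence. It could mean that only results after the second procedure are reported apart, or that a crossover analysis is added to a full comparison. This stands to the extent that a reader should not infer that the documents lay down an explicit exclusion; they do not. But the sentence contrasts patients with patients, not periods with periods, and no other text supports the milder reading. That reading would not rescue the plan either. A conventional repeated-measures ANOVA over all visits would tend to drop patients who have no 6-month value on their assigned treatment.

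A reader might also infer that any difference between arms biases the result, or that the bias always hides an effect. Neither follows. Selection acts on improvement from baseline, and bias needs a non-negligible share of unimproved patients as well as differing distributions. Step 3 shows that it can also create a difference.

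The magnitudes are assumed throughout. The protocol regards steroid supplementation as already known to be effective, so a mean fall of 1 point with 31% unimproved may be pessimistic. In the 3 vs 4 case the loss at 6 months is only 5% to 15%. This stands: the size in this trial is unknown and could be small.

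Finally, moving the primary time point to 3 months changes the question in a study built around six months of follow-up. This also stands, and it is the main cost of the simplest fix.

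**Conclusion.** The point holds as a conditional one, and it needs correcting because it concerns the primary comparison. On the most natural reading, patients unimproved at 3 months leave the PRGF-versus-steroid comparison, and the SAP has nothing that offsets this. The comparison is then biased at 3 months if a non-negligible share is unimproved and the arms differ in the mean, speed or spread of 3-month improvement. It is biased at 6 months to the extent that 3- and 6-month improvement are correlated. There is essentially no bias if almost nobody is unimproved, or if the arms share the same distribution of 3-month improvement and the same 3-to-6-month relation.

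Under the assumptions above, between 5% and 40% of a true 1.0-point difference is lost at 6 months, and 17% to 44% at 3 months. These figures should not be read as estimates for this trial: the documents fix neither size nor direction.

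**What to change.** Replace the protocol sentence on separate analysis, and put this in the SAP:

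> *The primary PRGF-versus-steroid comparison includes all randomised patients in their randomised arm, using pain at baseline, 1 and 3 months, all collected before any second procedure. The planned group-by-time ANOVA is run on these visits, and the primary contrast is the between-group difference in change from baseline to 3 months. Six-month results are secondary, and analyses restricted to patients who did not cross over are exploratory.*

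Fit the model so that a missed visit does not remove the patient, for example as a mixed model with the same group and time factors.

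If the sponsor keeps 6 months as primary, it should pre-specify one crossover strategy with its own wording, since the text above uses only data before a second procedure:
- **As randomised, including data after the second procedure.** This must be labelled as including that procedure's effect, and it dilutes the supplement contrast. If crossed-over patients gain the other arm's mean, the 1 vs 2 case gives (2 + 0.159 × 1) − (1 + 0.309 × 2) = 0.54, and 3 vs 4 gives 0.80. Both are further from 1.0 than the restricted comparison. It answers a different question, and it needs 6-month pain scores in crossed-over patients, which the protocol does not explicitly provide.
- **Crossover counted as failure or worst rank.** This needs no data after the second procedure. It does need a success definition for the other patients or a ranking rule, and a comparison of proportions or a rank test in place of the ANOVA.

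Cost: the 3-month option needs no new data, because 3-month pain is already scheduled for every patient. The wording change does alter the primary question, since the unconfounded contrast is then at 3 rather than 6 months. The SAP is dated January 2, 2025, and the documents do not say whether outcome data had been seen by then. If they had, the change should be reported as made after the fact. The clinical rule for a second procedure is not changed.

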Clinical Trial Number: NCT04731233

Title: A Randomized, Double-Blind Study of the Efficacy of Platelet-Rich Growth Factor (PRGF) Supplementation Compared to Steroid Supplementation After Temporomandibular Joint (TMJ) Arthrocentesis in Female Patients With TMJ Osteoarthritis (OA)

Date: January 2, 2025

Proposed Statistical Analyses

Statistical Analyses

Statistical analyses will consist of descriptive statistics (mean, standard deviation for parametric data; median and range for non-parametric data) and inferential statistics (two way ANOVA, 1 between (treatment groups), 1 within (time)) using a probability level of < 0.05). The primary outcome variable will be intracapsular pain.

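### Does the double-blind label need a masking procedure behind it before the plan can stand?

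*SAP*

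**What the plan says.** The SAP title describes "A Randomized, Double-Blind Study of the Efficacy of Platelet-Rich Growth Factor (PRGF) Supplementation Compared to Steroid Supplementation". The SAP's Statistical Analyses paragraph says nothing further on masking. It names intracapsular pain as the primary outcome and a two-way ANOVA (treatment between, time within) as the inferential analysis.

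The Protocol narrative describes the treatments and the visits:

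- PRGF is taken from the patient's "own blood and injected into the temporomandibular joint to activate stem cells".
- After arthrocentesis the patient receives "either a 2 cc steroid/bupivacaine hydrochloride supplementation (standard treatment group) or a 2 cc PRGF supplementation (experimental group").
- Follow-up visits are at 1, 3 and 6 months, "when the pain VAS measures and a clinical exam will be assessed".
- The switch rule reads "If patients have not experienced improvement in their primary outcome measure (TMJ pain) at the 3 month evaluation", and then "the patient will have a second TMJ arthrocentesis procedure that will be supplemented with the alternative medication/growth factors".
- For patients who switch: "Data from these patients will be analyzed separately from patients that complete the six month study".
- At 6 months "a second CBCT image of the temporomandibular joints will be obtained to determine the extent of bone remodeling within the TMJ".

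Neither document lists masked roles, a concealment method or a code holder.

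**The concern.** The label is doing work that no described procedure supports, and three features of this trial make masking harder than usual.

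1. One product is made from the patient's own blood. If blood were drawn in one arm only, patient and staff could infer the arm.
2. The products differ in nature: a steroid with a local anaesthetic against a plasma product. Appearance or early numbness could give the arm away.
3. At 3 months, someone must know the first allocation in order to supply the other product.

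The follow-up measures are a self-rated pain score and a clinical examination, and both can shift if the rater knows the arm. The 3-month pain result also determines who receives a second procedure and whose data are handled separately. Unmasked ratings could therefore affect both the scores and the make-up of the six-month comparison. A reader who has only the title cannot tell whether any of this was guarded against.

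**Working it through.** No formula applies, and the plan gives no figure to reproduce. The check is whether the text is silent or contradictory, and whether filling the silence would change anything.

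**Step 1: what is absent.** Count of word stems in the available text, ignoring case:

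| Stem | Protocol | SAP |
|---|---|---|
| blind | 0 | 1 (title) |
| random | 0 | 1 (title) |
| mask | 0 | 0 |
| conceal | 0 | 0 |
| alloc | 0 | 0 |
| syringe | 0 | 0 |
| code | 0 | 0 |
| blood | 1 (source of PRGF) | 0 |
| bupivacaine | 1 (steroid arm) | 0 |
| 2 cc | 2 (once per arm) | 0 |

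The factual claim holds: masking cannot be verified from this text. But *random* is also absent from the Protocol narrative, although the SAP title says the trial is randomized. The zeros reflect how brief the documents are and do not single out blinding.

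**Step 2: does any statement conflict with masked conduct?**

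| Point | What the text says | Conflict with double-blind? |
|---|---|---|
| Blood draw | PRGF comes from the patient's blood; nothing on whether the other arm is also drawn | None. Drawing from everyone is compatible with the text |
| Injectates | 2 cc in each arm; bupivacaine named for the steroid arm only | None. Equal volumes are compatible with masking; preparer and appearance are not addressed |
| 3-month switch | The alternative supplement is given | None. A preparer who holds the code can select it without telling patient, operator or examiner |
| Trigger for the switch | Lack of improvement in TMJ pain | None. No judge is described, and it may be a comparison of recorded scores |
| Outcome measures | Pain VAS and clinical exam | None. Both can be recorded by masked people |

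All five rows show silence, and none shows a contradiction.

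**Step 3: what would a masking paragraph alter?** The interventions, the three follow-up times, the separate handling of switched patients, the ANOVA and the 0.05 level would all stay as written. The planned analysis takes no input from the masking description.

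**Step 4: can a bias be sized?** That would need at least a rate of unmasking, the effect of unmasking on the pain score, and a standard deviation or sample size. The documents give none of these, so any figure would be invented.

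**The case for a change.** The strongest reply is that a title is an assertion and not a procedure. The Protocol narrative goes through consent, the procedure day, both injectates, follow-up, the switch and imaging, and is silent at each step where masking would have to operate. It lists a pregnancy test (below age 60), a questionnaire and an examination before the procedure, but no blood collection for PRGF in either arm. With a subjective primary outcome, a few sentences would settle the matter at little expense.

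Much of that stands. The narrative is silent, masking matters for a pain endpoint, and a reader would be better informed by a description. Three things limit it. First, title and consent pages are not part of the available text, and whether patients give blood is something a consent form could well describe; what is missing for that reason cannot be charged to the plan. Second, the argument shows that masking is unconfirmed, not that it is inadequate. Third, part of the weight is borrowed. Sorting patients by 3-month pain is an analysis-set question that exists even under perfect masking. A masked CBCT reader is a further inference, because the SAP names only pain as primary and mentions no CBCT analysis.

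**Conclusion.** No change to the plan follows. In the available text the double-blind claim rests on the SAP title alone, and masked roles, concealment, the blood draw and code custody at 3 months are not described. That is an omission of operational detail which a trial team fills in the ordinary course of running and reporting a trial under that title. No stated rule or number is shown to be wrong: of the five points compared, none conflicts with masked conduct. The size of any effect on the result cannot be derived from these documents.

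The conclusion assumes that the trial is run double-blind as its title says. If a role were in fact unmasked, the label would overstate what was done and the pain results would deserve more caution. That would be a finding about conduct, and nothing in the Protocol or SAP points to it.

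### The SAP's only inferential test, a group-by-time ANOVA, has no baseline-pain covariate, although pain is recorded before treatment

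*SAP*

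**What the plan says.** The SAP's Statistical Analyses section names one inferential procedure: "inferential statistics (two way ANOVA, 1 between (treatment groups), 1 within (time)) using a probability level of < 0.05". It adds "The primary outcome variable will be intracapsular pain". It lists no covariate. It does not say whether the pre-treatment value is a level of the time factor, which effect (group, time or their interaction) tests treatment, or which visit is primary.

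The protocol supplies the baseline value: "Pain and disability will be assessed using standard pain and physical measures that are recorded before and after treatment". On the procedure day patients "complete a questionnaire about their physical and pain symptoms and undergo a standardized clinical exam", and follow-up takes place "at 1 month, 3 months and 6 months when the pain VAS measures and a clinical exam will be assessed". Neither document mentions analysis of covariance, baseline adjustment or a change score.

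One more provision bears on the choice of visit. Patients whose TMJ pain has not improved at month 3 have a second procedure with the other supplement, and "Data from these patients will be analyzed separately from patients that complete the six month study".

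**The concern.** A patient's pain before treatment usually predicts pain afterwards. An analysis that estimates this relation removes that part of the between-patient variation from the treatment comparison. The planned ANOVA does not estimate it under any reading.

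- If time covers the follow-up visits only, baseline pain is unused (coefficient 0).
- If baseline is a level of time, the group main effect averages in a visit at which treatment can have had no effect. A constant effect then shrinks to 3/4 of its size. The group-by-time test compares changes, but spreads the comparison over 3 degrees of freedom.
- A 1-df change-from-baseline contrast inside that ANOVA recovers part of the loss, but fixes the coefficient at 1.

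At stake is power and interval width on the primary outcome. Separately, because the treatment test is unnamed, a reader cannot tell which p-value decides the trial.

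**Working it through.** **Inputs from the documents.** Two randomized groups; pain before treatment and at three follow-ups; significance level 0.05; no covariate. The documents give no sample size or power figure, so there is nothing to reproduce.

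**Assumptions (not trial figures).** n = 30 per arm, constant effect d = 0.5 SD at every follow-up, equal variances (SD = 1), equal correlation rho between all visits (compound symmetry), complete data. Rho is taken as 0.3, 0.5 and 0.7.

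**Variances.** For the mean of k follow-ups, v = (1 + (k−1)rho)/k.

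- Baseline unused: v
- Change from baseline: v + 1 − 2rho
- Baseline as covariate: v − rho²

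The covariate therefore lowers the variance by rho² against the first and by (1 + rho² − 2rho) = (1 − rho)² against the second, before the cost of estimating the slope.

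**Power.** Noncentral F with noncentrality (n/2)d²/variance and 1 numerator df; denominator df 2n−2 without and 2n−3 with the covariate. Example for one visit at rho 0.5: 15 × 0.25/1 = 3.75, power 0.48; adjusted 15 × 0.25/0.75 = 5.00, power 0.59.

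| Comparison (rho 0.3 / 0.5 / 0.7) | Baseline unused | Change | Covariate |
|---|---|---|---|
| One visit | 0.48 / 0.48 / 0.48 | 0.36 / 0.48 / 0.69 | 0.51 / 0.59 / 0.76 |
| Mean of months 1 and 3 | 0.66 / 0.59 / 0.54 | 0.46 / 0.59 / 0.81 | 0.72 / 0.77 / 0.89 |
| Mean of all three | 0.74 / 0.65 / 0.57 | 0.51 / 0.65 / 0.85 | 0.82 / 0.84 / 0.93 |

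The variance reduction against baseline unused is 9/25/49% for one visit and 14/33/58% for months 1 and 3. Against change it is 35/25/15% and 47/33/20%. The last row treats month 6 as an ordinary visit, which the crossover makes doubtful.

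**Baseline as a fourth time level.**

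- Group main effect: size 0.75d, variance (1 + 3rho)/4, power 0.54/0.44/0.37.
- Group-by-time: noncentrality (n/2)(0.75d²)/(1 − rho) = 4.02/5.62/9.38 on 3 and 174 df, power 0.35/0.48/0.72.
- Like for like on 3 df, a joint baseline-adjusted test of the three follow-ups has noncentrality 8.46/9.00/12.10 and, with the conservative denominator df 2n−3, power 0.65/0.68/0.82.
- With no effect at month 1 and 0.5 SD afterwards, the adjusted joint test has 0.58/0.68/0.86 against 0.46/0.61/0.85 for group-by-time.

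**Cost of estimating the slope.** The adjusted variance is inflated by 1 + 1/(2n−4) = 1 + 1/56, about 1.8%. Net one-visit reductions against baseline unused become 7/24/48%. At rho = 0, power falls only from 0.478 to 0.471.

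**Other sample sizes.** At rho 0.5, one visit, moving from 20 to 60 per arm takes power without adjustment from 0.34 to 0.78, and with it from 0.43 to 0.88. For 80% power at one visit (normal approximation), rho 0.3/0.5/0.7 requires 58/48/33 per arm with the covariate, 63/63/63 with baseline unused and 88/63/38 with change.

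**Unnamed test.** Under compound symmetry the group and group-by-time F tests are independent under the null. If either may be claimed at 0.05, type I error is 1 − 0.95² = 9.75%; simulation of 100,000 null trials per setting gave 0.096 to 0.098.

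**The case against.** The ANOVA is a valid analysis of a randomized trial, so the point concerns efficiency only. Since the SAP has a within-patient time factor and the protocol measures pain before and after treatment, the natural reading is that baseline is one level of time. The fair comparators are then the change contrast and group-by-time, not the analysis that ignores baseline. Against these the gain is modest when rho is high: at 0.7, one visit, 0.69 becomes 0.76, and for a late effect on 3 df 0.85 becomes 0.86. This stands as a limit on size. It does not reverse the direction, and on that reading the gain is large at low rho (0.36 to 0.51 at rho 0.3).

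The calculation also favours adjustment slightly. The tabulated adjusted powers omit the 1.8% estimation cost; with it, one visit gives 0.507/0.587/0.752. A change contrast inside the ANOVA could use the pooled error on 3(2n−2) df, giving 0.370/0.486/0.701. Each correction is about 0.01, and the ordering survives both.

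The remaining limits stand. No magnitude comes from the trial, equal correlation is assumed, and a weaker correlation with month 6 was not explored. The three-visit gains are the least applicable, because non-improvers receive the other supplement after month 3 and are analysed separately. The 9.75% depends on someone claiming either effect, which the SAP neither allows nor excludes, and it is not a ceiling: a simulation with autoregressive correlation (30 per arm, four times, rho 0.7) gave about 0.107. It is a separate matter and adds nothing to the weight of the covariate point.

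**Conclusion.** The concern holds. The plan is valid but less precise than its own data allow, and no reading of the time factor makes good the whole loss. The figures that fit this design best are those for one visit and for months 1 and 3. Across rho 0.3 to 0.7, adjustment cuts the variance by 9 to 58% against ignoring baseline and by 15 to 47% against a change score, before an estimation cost of about 1.8% at 30 per arm. These percentages rest on equal variances and equal correlations; the powers rest in addition on the assumed 0.5 SD effect and 30 per arm. Nothing here implies bias. The change should be made, but the trial's validity does not depend on it. The unnamed treatment test is a secondary gap that the same revision can close.

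**What to change.** Replace the two-way ANOVA with a repeated-measures model in which post-treatment pain is the outcome, arm, visit and arm-by-visit are factors, and baseline pain is a covariate. Name one between-arm contrast as the primary test before unblinding, and report it with a 95% CI. The visit or visits are for the sponsor to choose. That choice depends on when the effect is expected, and it must take account of the change of supplement after month 3 for non-improvers and their separate analysis.

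The cost is a revised SAP paragraph and a few lines of code, with no new data and no effect on patients. The documents do not say whether outcome data have already been seen; if they have, the revision should say so.
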